## **6. RESEARCH QUESTION AND OBJECTIVE(S)**

### **6.1. Primary Objectives**

The primary aim of this study is to evaluate the effectiveness of the aRMMs for CAB-LA within Canada, specifically addressing HC's request. More specifically, the primary objectives are to evaluate:

1. Whether HCPs and CAB-LA users have used aRMMs for CAB-LA (Prescribers' Guide, Prescribers' Checklist, User Guide, Injection Appointment Reminder Card);
2. HCP knowledge of key CAB-LA risk messages within the HCP-specific aRMMs (Prescribers' Guide and Prescribers' Checklist);
3. User knowledge of key CAB-LA risk messages within the user-specific aRMMs (User Guide and Injection Appointment Reminder Card);
4. HCP (prescribers') attitudes regarding the importance of selecting individuals who will adhere to the CAB-LA dosing schedule and attend follow-up visits; and
5. HCP and user behaviours as they relate to key CAB-LA risk messages within the aRMMs.

## 6.2. Secondary Objectives

The secondary objectives are additional research objectives, not an HC-mandated requirement. The secondary objectives are to:

Among HCPs who prescribe or administer CAB-LA, describe:

1. Decision-making process regarding the choice between oral PrEP and CAB-LA;
2. Experience implementing, prescribing, or managing CAB-LA and oral PrEP in clinical practice and among individuals eligible for PrEP, including HIV-testing;
3. Use of CAB-LA oral lead-in and oral bridging;
4. Management of PK tail among those who discontinue CAB-LA; and
5. Attitudes towards CAB-LA.

Among CAB-LA users, describe:

6. Demographic and clinical characteristics;
7. Decision-making process regarding the choice between oral PrEP and CAB-LA;
8. Experience using CAB-LA, including satisfaction and acceptability of the CAB-LA regimen, PrEP-related preferences, any benefits or limitations of HCP visit schedule, emotional and daily impact of using CAB-LA, and experience of stigma for using PrEP, including CAB-LA; and
9. Utilization patterns, including adherence and persistence, use of and acceptability of CAB-LA oral lead-in and oral bridging, rates of discontinuation, and reasons for discontinuation.

## 7. RESEARCH METHODS

### 7.1. Study Design

This is an observational study consisting of cross-sectional surveys and a retrospective database analysis based on the study objectives outlined above.

#### Primary Objectives

A cross-sectional survey will be conducted among HCPs and CAB-LA users and will involve primary data collection (KAB survey). The KAB survey will be conducted at one time point corresponding to 18-months +/- 2-month post CAB-LA launch (July 15, 2024), with data collection occurring from December 2025 to April 2026. As the survey is cross-sectional, there will be no follow-up surveys, i.e., no pre-index or post-index follow-up data will be collected. The data collection start date for the KAB survey will be dependent on the final protocol approval date by HC, and may occur later (i.e., between January 2026 to May 2026).

#### Secondary Objectives

For the secondary objectives 1 through 8, primary data will be collected through surveys administered to HCPs and CAB-LA users (see Table 1). The HCP and user surveys will be conducted at one time point corresponding to approximately 18-months +/- 2-month post CAB-LA launch (December 2025 to April 2026).

For secondary objectives 6 and 9 a retrospective cohort analysis will be executed using data from the CAB-LA patient support program (“Apretude Supports Program”) database (Table 1), which captures basic CAB-LA use information for all individuals enrolled in the program. In the Apretude Supports Program database, data will be included for individuals initiating CAB-LA between 15 July 2024 (the date of commercial availability in Canada) and October 2026 (the ascertainment period). Within this ascertainment period, eligible individuals will be indexed into the cohort at the date of initiation of CAB-LA injections. An ascertainment period end date of October 2026 was chosen to allow for a minimum 1-year follow-up from initiation of CAB-LA (index date) given final analysis will take place November 2027. An interim analysis is planned for Q1/Q2 2026 for data available up to that time point (July 2024 to Q1/Q2 2026).

Two separate sources of CAB-LA user demographic data will be available in this study to address secondary objective 6: one from the CAB-LA user survey and one from the Apretude Supports Program database. If linkage between the survey data and PSP database is feasible, the analysis will aim to combine the data to gain further insights particularly in regards to user factors impacting utilization patterns. The CAB-LA user survey data will be used to explore relationships between demographic characteristics and objectives 7 and 8, while the Apretude Supports Program data will inform analyses related to objective 9.

**Table 1. Study objectives and data collection matrix**

Secondary objectives		Primary data collection		Secondary data collection
		HCPs survey	CAB-LA users survey	Retrospective Cohort Data Analysis (from Apretude Supports Program)
1	Decision-making process regarding the choice between oral PrEP and CAB-LA	X		
2	Experience implementing, prescribing, or managing CAB-LA and oral PrEP in clinical practice and among individuals eligible for PrEP, including HIV-testing	X		

[figure not shown]
3	Use of CAB-LA oral lead-in and oral bridging	X		
4	Management of PK tail among those who discontinue CAB-LA	X		
5	Attitudes towards CAB-LA	X		
6	Demographic and clinical characteristics		X	X
7	Decision-making process regarding the choice between oral PrEP and CAB-LA		X	
8	Experience using CAB-LA, including satisfaction and acceptability of the CAB-LA regimen, PrEP-related preferences, any benefits or limitations of HCP visit schedule, emotional and daily impact of using CAB-LA, and experience of stigma for using PrEP, including CAB-LA		X	
9	Utilization patterns, including adherence and persistence, use of and acceptability of CAB-LA oral lead-in and oral bridging, rates of discontinuation, and reasons for discontinuation			X

### 7.1.1. Study Schematic

#### Primary Objectives

The survey will address the five primary objectives. A study design schematic is shown in Figure 1.

**Figure 1. Study schematic for cross-sectional HCP and user survey**

[figure not shown]
**Abbreviations:** Apr, April; Dec, December; HCP, Healthcare provider.

\*Exact timing of data collection will be adjusted based on Health Canada protocol review timelines

### Secondary Objectives

[figure not shown]
The survey will address secondary objectives 1-8 (Figure 2). The retrospective database analysis will address secondary objectives 6 and 9 (Figure 3).

**Figure 2. Study schematic for secondary objective survey and retrospective database analysis**

**Abbreviations:** Apr, April; Dec, December; HCP, Healthcare provider; PSP, Patient support program.

**Figure 3. Study schematic for retrospective database analysis (Apretude Supports Program)**

**Abbreviations:** CAB-LA, Long-acting injectable cabotegravir

## 7.2. Study Population and Setting

### HCPs

The HCP study population will comprise physicians, nurses, and pharmacists who prescribe CAB-LA or who manage CAB-LA use among CAB-LA users in Canada. For example, not all nurses and pharmacists are able to prescribe CAB-LA (some may be able to prescribe by way of a medical directive); however, these HCPs may still have experience administering CAB-LA and managing care of CAB-LA users. For questions specific to prescribing decisions, the question will only be asked of prescribers.

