Due to the risk of drug resistance with use of CAB-LA in undiagnosed HIV-1 infection, HC requested the use of additional risk minimization measures (aRMMs) in the form of an Education Program (consisting of a Prescribers' Guide, Prescribers' Checklist, User Guide and Injection Appointment Reminder Card) to be implemented for HCPs prescribing and administering CAB-LA and CAB-LA users. The Prescriber Guide contains information regarding use of CAB-LA as an overall HIV-1 infection prevention strategy and optimal use of CAB-LA providing detail on potential risks, consideration of alternative forms, importance of counselling, recommendations for ensuring adherence and dosing regimens, and suggestions for when doses are missed. The Prescribers Checklist details the list of reminders HCPs should discuss with CAB-LA users at initial and follow-up visits, including reminders for evaluation, counselling, checking clinical symptoms, and adherence. The User Guide relays important information to individuals at risk of HIV infection regarding what they need to know prior to starting, when taking and when discontinuing CAB-LA. The Injection Appointment Reminder Card provides details regarding date of injection visit, importance of strict adherence, and the emergency contact information in case of troublesome symptoms and side effects. The aRMMs are available primarily online at the Apretude Resource Portal website available in English and French.

These aRMMs have distinct key risk messages which include 1) CAB-LA should be used as part of a comprehensive prevention strategy; 2) there is potential risk of HIV-1 drug resistance development in individuals with undiagnosed HIV-1 infection; 3) strict adherence to the recommended dosing schedule is important to reduce risk of HIV-1 infection and the potential development of resistance and 4) regular monitoring and testing is needed to confirm HIV-1 status prior to starting and during CAB-LA use.

Per HC's request, a Knowledge, Attitude and Behaviour (KAB) study is needed to evaluate the effectiveness of these aRMMs based on pre-defined success thresholds for knowledge and behaviour among this population regarding key risk messages.

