### HCP Survey

From the HCP survey, data will be collected on:

Table 5. Outcome assessment areas in HCP survey

Domain	Subdomain	Survey Topic
Experience with prescriber aRMMs	Prescribers' Guide / Checklist / Reminder Card*	
 
• Prior access to aRMM
 

Knowledge	Comprehensive HIV-1 infection prevention strategy	
 
• Knowledge of additional prevention strategies
 

	Risk of developing drug resistance	
 
• Knowledge of risk of developing resistance to CAB-LA if user acquires HIV-1 before or while taking CAB-LA or following discontinuation of CAB-LA
 
• Steps to take with suspected or confirmed HIV-1 infection in CAB-LA user
 
• Knowledge of the presence of residual concentrations of CAB-LA following discontinuation
 
• Steps when user discontinues CAB-LA; considering alternative forms of PrEP for those at risk of HIV-1 infection
 

	Importance of CAB-LA adherence	
 
• Knowledge of the importance of careful selection of individuals who agree to the CAB-LA dosing schedule
 
• Knowledge of appropriate use of oral cabotegravir including for bridging
 
• Steps when user misses oral cabotegravir dose or an injection appointment
 

	Regular monitoring/HIV-1 seroconversion	
 
• Knowledge of testing requirements for HIV-1 infection prior to initiating CAB-LA, and with each subsequent injection of CAB-LA
 

Attitudes	Importance of CAB-LA adherence (prescribers only)	
 
• HCP prescribers' perspective on the ideal adherence patterns for individuals being considered to receive CAB-LA
 

#{vault:document\_date\_\_v}

Protocol for Non-Interventional Studies PASS Studies and Non-PASS Studies (4.0) March 2024

Template Doc ID: TMF-15706807

Parent Doc ID: VQD-SOP-066694

Domain	Subdomain	Survey Topic
Behaviours	Comprehensive HIV-1 infection prevention strategy (prescribers only)	
 
• Frequency of counseling on additional prevention strategies
 
• Frequency of counseling on use of the User Guide and Patient Medication Information to gain more information
 

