	Risk of developing drug resistance	
 
• HIV-1 status confirmation prior to prescribing CAB-LA and throughout use (prescribers only)
 
• Frequency of counseling on steps if individual has suspected or confirmed HIV (prescribers only)
 
• Frequency of counseling on alternative forms of PrEP among individuals considering discontinuation of CAB-LA (prescribers only)
 
• Frequency of commencing antiretroviral therapy or referring for HIV treatment among individuals with suspected or confirmed HIV-1 diagnoses
 

	Importance of CAB-LA adherence (prescribers only)	
 
• Frequency of carefully selecting individuals who will adhere to the CAB-LA dosing schedule prior to prescribing
 
• Frequency of counseling on importance of adherence to dosing schedule
 
• Frequency of counseling on booking next appointments
 

	Regular monitoring/HIV-1 seroconversion	
 
• Frequency of risk assessment and HIV-1 testing (prescribers only)
 
• Frequency of counseling on importance of regular HIV screening (prescribers only)
 
• Steps taken when user misses a scheduled injection visit (not part of KAB scoring)
 

	Management of those with suspected or confirmed HIV	
 
• Steps taken for suspected/confirmed HIV
 

\* The question in the HCP survey about the Reminder Card specifically asks if the HCP or any member of their care team has ever accessed the Apretude Injection Appointment Reminder Card, which they provide to Apretude users (this question is not scored, it is

only included to better understand HCPs’ general experience of accessing Apertude aRMMs).

The full list of variables for the HCP primary objective survey are available in Annex 2.

User survey

From the user survey, data will be collected on:

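### Table 5 limits 10 of 12 scored HCP behaviour topics to prescribers, while objective 5, the success cut-off and the stated precision refer to all HCPs

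*Protocol*

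**What the plan says.** Section 7.2 (HCPs) gives the only general rule on who is asked what: "For questions specific to prescribing decisions, the question will only be asked of prescribers". Just before it, the section explains why HCPs who cannot prescribe are enrolled: "these HCPs may still have experience administering CAB-LA and managing care of CAB-LA users". Section 5.2 describes the education program as "to be implemented for HCPs prescribing and administering CAB-LA and CAB-LA users".

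Table 5 (section 7.3.2) sets the restriction topic by topic. Two behaviour subdomains are closed to non-prescribers as a whole. One is labelled "Comprehensive HIV-1 infection prevention strategy (prescribers only" and contains, for example, "Frequency of counseling on additional prevention strategies". The other is adherence, which contains "Frequency of counseling on booking next appointments". In the remaining subdomains single topics carry the label, such as "Frequency of counseling on steps if individual has suspected or confirmed HIV (prescribers only" and "Frequency of counseling on importance of regular HIV screening (prescribers only".

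Primary objective 5 (section 6.1) and the definition of behaviours in section 7.3.2 refer to HCPs without this limit. Objective 4 and the attitude outcome, by contrast, are expressly confined to prescribers. The assessment of success in section 7.3.2 asks for at least 80% appropriate answers within a domain for each person, and for at least 70% of HCPs to reach that level. Section 7.5.2 stops recruitment of non-prescribers at 50 of the 100 HCPs. Section 7.5.1 gives ±9.8% as the maximum for HCPs.

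**The concern.** Section 7.2 suggests that non-prescribers are left out only of questions about the decision to prescribe. Table 5 also leaves them out of counselling on prevention, the User Guide, the dosing schedule, appointment booking and HIV screening, none of which is a prescribing decision in the ordinary sense. The outcome is still called HCP behaviour and is judged against a cut-off for HCPs.

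This outcome answers a regulator-mandated primary objective. If the two groups answer different sets of items, a single pooled success percentage has no clear meaning. The precision stated for 100 HCPs also does not apply to items that perhaps only 50 of them answer.

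**Working it through.** **1. The plan's own precision figure.** Half-width = 1.96 × √(p(1−p)/n). With n = 100 and p = 0.50 this is 1.96 × √(0.25/100) = 9.8 percentage points, as stated in section 7.5.1. At p = 0.70 it is 9.0, as in Table 13.

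**2. Count of HCP behaviour topics in Table 5.** A topic counts as restricted if it or its subdomain is marked for prescribers only. It counts as scored unless marked otherwise; only the missed-visit topic is.

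| Subdomain | Topics | Prescribers only | Open, not scored | Open, scored |
|---|---|---|---|---|
| Comprehensive prevention | 2 | 2 | 0 | 0 |
| Drug resistance | 4 | 3 | 0 | 1 |
| Adherence | 3 | 3 | 0 | 0 |
| Monitoring | 3 | 2 | 1 | 0 |
| Management of suspected or confirmed HIV | 1 | 0 | 0 | 1 |
| Total | 13 | 10 | 1 | 2 |

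Restricted share: 10/13 = 77% of all topics and 10/12 = 83% of scored topics. Seven of the ten are counselling topics. The other three are status confirmation, patient selection, and risk assessment with HIV testing. The two open scored topics are starting or referring for HIV treatment and the steps taken for suspected or confirmed HIV.

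**3. What the 80% threshold then means.** Assume one question per topic.
- Prescriber: 0.8 × 12 = 9.6, so 10 of 12 are needed.
- Non-prescriber, skipped items left out: 0.8 × 2 = 1.6, so 2 of 2 are needed.
- Non-prescriber, skipped items counted as not optimal: at most 2/12 = 17%, so the threshold cannot be reached.

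The denominator rule in section 7.7.1.1 (only those who answered) points to leaving them out.

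**4. Effect on the 70% cut-off.** With 50 prescribers and 50 non-prescribers, pooled success = 0.5 × P + 0.5 × N, where P and N are the success percentages in the two groups. The limits are:
- N = 100%: the cut-off is met once P reaches (70 − 50)/0.5 = 40%.
- N = 0%: the pooled figure is at most 50%, a failure even if P = 100%.

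These are bounds, not forecasts. They show that the verdict can turn on two topics answered by half the sample.

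**5. Precision on the restricted items.** The number of prescribers can lie between 50 and 100. At n = 50, 1.96 × √(0.25/50) = 13.9 points at p = 0.50, and 12.7 at p = 0.70. Both stand in the n = 50 row of Table 13. The range at p = 0.50 is therefore ±9.8% to ±13.9%.

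**6. Reporting by HCP type.** Table 14 sets no prescriber minimum within nurses or pharmacists. A sample of 50 prescribing physicians and 50 non-prescribing nurses and pharmacists meets the minimums for prescriber status and HCP type. In that sample no nurse or pharmacist answers any of the ten restricted topics, although sections 7.7 and 7.10 plan to compare HCP types.

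**The case against.** **No literal contradiction.** A reader might infer that section 7.2 sends every other question to all HCPs. It does not say so. It limits who answers prescribing questions and is silent on the rest, and Table 5 labels its restrictions openly. Both can be followed. This stands: the fault is one of scope.

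**Measuring prescribers is defensible.** The HCP materials are titled for prescribers, and behaviour is defined as carrying out their recommended actions. That supports restricting some items. It does not explain why the objective, the behaviour definition and the cut-off remain stated for all HCPs, or why the knowledge topics on the same messages carry no restriction.

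**Who does these tasks is not stated.** A reader might infer that non-prescribers carry out all the restricted tasks at injection visits. Section 7.2 says only that they may have experience of administering CAB-LA and managing care. The point cannot rest on that inference.

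**Non-prescriber practice is not wholly unmeasured.** Table 9 collects frequency of HIV testing and counselling on residual drug levels without restriction, the missed-visit topic is open to all, and users report discussions with their HCPs. A claim that poor practice could never be detected would go too far. These data do not enter the HCP behaviour score, however.

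**The share by question cannot be checked.** Table 7 lists 2 + 3 + 3 + 7 = 15 HCP behaviour questions and marks none as prescriber-only, and the survey in Annex 2 is not shown. This stands, so the 83% is a share of topics. Likewise, 50 non-prescribers is a cap, not an expected number.

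**Precision.** Section 7.5.1 names objectives 2 to 4 as its focus and does not list objective 5. It then states the HCP maximum for the primary objective without exception, and objective 4 is itself confined to prescribers, so the n = 50 case arises there too.

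**Conclusion.** The point holds as a mismatch in scope with consequences for a primary outcome. By topic, 10 of 12 scored HCP behaviour topics are closed to non-prescribers, who may be half of the respondents and would be scored on two topics about suspected or confirmed HIV. The pooled HCP behaviour result then combines two different scores. Precision on the restricted items can be as poor as ±13.9%, against a stated maximum of ±9.8%.

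This rests on Table 5 being followed as written in the survey routing. The 10-of-12 against 2-of-2 comparison also assumes one question per topic, and the ±13.9% assumes the minimum of 50 prescribers; with more prescribers both the mixing and the loss of precision shrink. The documents do not support reading this as a direct contradiction, or as proof that practice among non-prescribers goes unobserved.

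**What to change.** Reconcile section 7.2, Table 5 and primary objective 5 before launch, and mark in Table 7 which questions are for prescribers only.

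- **Preferred:** put the counselling items that are not prescribing decisions to every HCP who administers or manages CAB-LA, with a *not part of my role* answer that is left out of the score.
- **Otherwise:** keep the restriction and label the outcome as prescriber behaviour in the objective, the definition and the success criterion.
- **In either case:** report the behaviour items and the 80%/70% success result separately by prescriber status, with denominators, and restate the precision for prescriber-only items as up to ±13.9%.

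The cost is a few more survey minutes for non-prescribers, a routing change that may need review before launch, and a less favourable stated precision. The *not part of my role* answer makes the number of scored items vary between people, which is a further reason to give denominators. No extra respondents are needed.

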### CAB-LA Users

For the survey component of the study, CAB-LA users will be recruited from different clinical settings where they access PrEP (for example, but not limited to hospitals, outpatient clinics, and pharmacies) across Canada. For the retrospective database analysis, data from the Aprelude Supports Program will be used. Due to the logistical barrier of research ethics boards (REB) typically requiring parental/guardian consent in order for minors to participate in research, adolescent CAB-LA users ( $\geq 16$  years of age) may experience barriers to participation in the survey driven by fears about parent/guardian access to sensitive information, their potential disapproval, and interpretation of their participation as being sexually active or lesbian, gay, bisexual, transgender or queer (LGBTQ); fear of being ‘outed’, stigmatized, or punished by their families. Thus, a waiver of parental/guardian consent will be requested with the appropriate REBs in order to reduce such barriers to adolescent participation. If the waiver is granted, adolescent

CAB-LA users will be considered for inclusion in the survey component. Otherwise, CAB-LA users must be at least 18 years of age in order to be considered for inclusion in the survey component. For the retrospective data analysis, users of all ages will be considered for inclusion.

## Setting

For the survey component of the study, the setting will be web-based (online). For the retrospective analysis, the study setting will include various Apretude Supports Program sites across Canada: As of April 21, 2025, there are 159 sites across Canada, with sites distributed between Ontario (78), Quebec (40), British Columbia (15), Alberta (9), New Brunswick and Saskatchewan (5 each), Manitoba and Nova Scotia (2 each), and one site each in Newfoundland and Labrador, Prince Edward Island, and the Northern Territories. The Apretude Supports Program is designed to facilitate access and provide assistance to qualifying individuals who have been prescribed CAB-LA. The services under the program may include reimbursement investigation and/or financial assistance, assistance with drug administration, medication dispensing, medication delivery or testing, and disease and medication resources. This Program is a ViiV initiative and is administered by third-party service providers, specifically Bayshore Speciality Rx Ltd, selected by ViiV.

